FINAL REPORT

**EFFECT OF LIRAGLUTIDE ON EPICARDIAL FAT
IN SUBJECTS WITH TYPE 2 DIABETES**

INVESTIGATOR-INITIATED STUDY

NCT 2014740

University of Miami Clinical Trial # 20120811

[name] [name]

Professor of Clinical Medicine

Director of University of Miami Hospital Diabetes Service

Division of Endocrinology, Diabetes and Metabolism, Department of Medicine,
University of Miami, Miller School of Medicine, Miami, FL, USA

[contact]

SUMMARY

Background Epicardial adipose tissue (EAT) is a peculiar visceral fat depot with anatomical and functional contiguity to the myocardium and coronary arteries. EAT is a highly inflammatory tissue enriched with genes involved in endothelial function, coagulation, immune signalling, lipid metabolism, potassium transport and apoptosis. EAT is associated with coronary artery disease, diabetes and obesity. EAT is easily measurable and an emerging therapeutic target that responds and modifies to medications targeting the adipose tissue. Liraglutide, an analogue of glucagon-like peptide-1 (GLP-1), is indicated for the treatment of type 2 diabetes mellitus. Liraglutide has recently shown to reduce cardiovascular risk. Nevertheless, whether liraglutide could reduce EAT is unknown.

Aim The primary objective of this interventional study was to evaluate whether liraglutide can cause a significant and rapid reduction of EAT, organ-specific visceral fat and cardiovascular risk factor itself, in overweight/obese type 2 diabetic patients.

Methods To test this hypothesis we performed a 6-month randomized, open-label, controlled study in 100 type 2 diabetic subjects with body mass index (BMI) $\geq 27 \text{ kg/m}^2$ and HemoglobinA1c (HbA1c) $\leq 8\%$ on metformin monotherapy. Individuals were randomized in 2 groups to receive additional liraglutide up to 1.8 mg sc once daily ($n=55$) or to remain on metformin up to 1000 mg twice daily ($n=45$). Ultrasound-measured EAT thickness was measured at baseline, 3 and 6-month follow ups.

Results In the liraglutide group EAT decreased from 9.6 ± 2 to 6.8 ± 1.5 and 6.2 ± 1.5 mm ($p < 0.001$), accounting for a -29% and -36% of reduction at 3 and 6 months, respectively, whereas there was no EAT reduction in the metformin group; BMI and HbA1c improved only in the liraglutide group after 6 months.

Conclusions. For the first time, we found that liraglutide added to metformin caused an unprecedented, close to 40%, reduction of EAT. EAT reduction was not only quantitatively important, but also very rapid, as the earliest reduction, of almost 30%, occurred within 3 months. We suggest that the recently reported (LEADER study) beneficial cardiovascular effects associated with liraglutide treatment may be EAT-mediated.

PROTOCOL

STUDY RATIONALE

This study was designed to reflect a real-life and common clinical scenario of type 2 diabetic patients presenting with fairly good glucose control, but at mild-moderate cardiovascular risk. We intentionally chose HbA1c $\leq 8\%$ to rule out the confounding effect of a poor diabetes control on study outcomes. Also, as prior treatment with metformin was a criteria for entry into the study, we could evaluate the independent effect of liraglutide on EAT. Epicardial fat has recently shown to be a modifiable and measureable cardiovascular risk factor, and therefore it could well serve as primary outcome of the study. In addition, EAT is known to be higher in subjects with diabetes, due to its strong correlation with visceral adiposity and insulin resistance.

METHODS

Study design

This was a randomized, open-label controlled 6-month study in 100 overweight/obese (body mass index (BMI) $\geq 27 \text{ kg/m}^2$) type 2 diabetic subjects on metformin monotherapy. Patients were screened among those routinely referred to the Division of Endocrinology, Diabetes and Metabolism out-patient clinic at the University of Miami. Approximately 500 patients were screened between January 2014 and January 2016. All the patients provided written informed consent before participation. The study was approved by the University of Miami Institutional Review Board (# 20120811) and conducted in accordance with the Declaration of Helsinki and Good Clinical Practice guidelines.

Study Criteria and Treatment Arms

Patients were enrolled on the basis of the following inclusion criteria: type 2 diabetes, HbA1c $\leq 8\%$ measured at least 1 month prior to the study, BMI $\geq 27 \text{ kg/m}^2$, prior treatment with metformin only, age ≥ 18 and ≤ 65 years old. Exclusion criteria were the following: type 1 diabetes, current use of insulin, other GLP-1 receptor agonists, dipeptidyl peptidase 4 (DPP-4) inhibitors, pramlintide, sulfonylureas, thiazolidinediones, history of diabetic ketoacidosis, history of diabetic macro or micro vascular complications, known contra-indications to liraglutide, such as previous history of pancreatitis or medullary thyroid carcinoma, personal or family history of multiple endocrine neoplasia type 2, renal or liver or heart failure, acute or chronic infective diseases, cancer or chemotherapy, current use of systemic corticosteroids or in the 3 months prior this study, known or suspected allergy to liraglutide, excipients, or related products, pregnant, breast-feeding or the intention of becoming pregnant. Eligible individuals were randomly assigned to receive additional liraglutide, or to remain on metformin. The liraglutide-group was started on liraglutide (Victoza®) up to 1.8 mg s.c. once daily. Liraglutide was administered with a starting dose of 0.6 mg (for a least one week) and subsequent increments to 1.2 mg (after a least one week) and to 1.8 mg (after at least a week on 1.2 mg). Liraglutide-group subjects had to achieve the final dose of 1.8 mg by at least three weeks from the starting dose. Subjects who were not able to tolerate the dose of 1.8 mg, were advised to lower the dose to 1.2 mg. Patients received full training and titration

instructions by a registered nurse. Metformin regimen was continued. Metformin-group was treated with metformin monotherapy for the duration of the study at the dosage from 500 mg twice daily to a maximum of 1000 mg twice daily. Both groups received lifestyle and diabetes education, as part of the standard care. Patients in both groups were advised to continue with their usual dietary habit and physical activity. Once patient eligibility and written consent were obtained, the study participants were scheduled for the baseline clinic visit. Each patient underwent a transthoracic echocardiographic study, full physical examination and a fasting blood drawn for measurement of blood glucose and haemoglobinA1c (HbA1c) and other parameters. Study patients were then scheduled for follow-up visits at 3 and 6 months and the same visit procedures were repeated at each follow-up visit.

Study procedures

Echocardiographic Epicardial Fat Thickness. EAT thickness was measured according to the method first described and validated by Iacobellis et al. Briefly, EAT was identified as the echo-free space between the outer wall of the myocardium and the visceral layer of pericardium. EAT thickness was measured perpendicularly on the free wall of the right ventricle at end-systole in three cardiac cycles. Maximum EAT thickness was measured at the point on the free wall of the right ventricle along the midline of the ultrasound beam, perpendicular to the aortic annulus, used as the anatomical landmark for this view. The average value of three cardiac cycles was calculated and used for analysis. Echocardiograms were done by an experienced operator who was blinded to the patients' data. Intra-observer reproducibility of echocardiographic measurement of EAT was assessed by the intra-class correlation coefficient.

Physical Examination All anthropometric measures were obtained by the study nurse at each visit. Height (in cm) and weight (in kg) were measured, and BMI was automatically calculated as weight in kilograms divided by the square of height in meters (kg/m^2). Blood pressure was measured in the seated position, using an automated cuff and digital readout, and entered by the study nurse into the electronic database. Resting heart rate was also measured

Blood Measurements Fasting blood samples for fasting blood glucose (FBG) and HbA1c were obtained from all individuals according to the study design timetable. Blood parameters were measured according to standard and previously described procedures. Fasting comprehensive metabolic panel and lipid profile were also measured at each visit as standard diabetes care.

Follow up of glucose profile Study patients were advised to monitor their capillary glucose twice daily, fasting in the morning and post-prandially. Glucose profile was tracked weekly by the research coordinator and/or principal investigator who were in contact with study patients throughout MyUHealth e-mail system or by telephone.

STATISTICAL ANALYSIS

Primary outcome of the study was EAT changes on liraglutide combined to metformin vs metformin monotherapy; secondary outcomes were determinants of HbA1c changes during treatment. Assuming a difference of 1 ± 0.5 mm in EAT to be clinically significant and using a significance level of $p<0.05$ and 90% power, the current study sample size was sufficient to detect statistical significant differences in EAT between liraglutide and metformin group. Continuous variables were considered as age-adjusted and sex-adjusted means with their standard deviations (SDs). Patients were randomized consecutively using a computer generated randomization table. Two-sample t test with 95 % CI for difference was performed to evaluate differences between the two groups at baseline. Two-way ANOVA was used to calculate changes (Δ) in EAT and other study variables between baseline, 3 and 6 months in both groups. Relations between study variables were calculated using simple linear regression analysis. Two-tailed $p < 0.05$ indicates statistical significance. Statistical analysis was performed using Minitab 17 Software.

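### The primary outcome is a between-group change in EAT, but the report gives EAT figures for the liraglutide arm only and headlines a within-arm change, rounded up, as the treatment effect

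*Combined protocol and SAP*

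**What the plan says.** The Statistical Analysis section defines the target as a comparison between arms: "Primary outcome of the study was EAT changes on liraglutide combined to metformin vs metformin monotherapy".

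The same section names two analyses that bear on it:

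- For group differences at entry: "Two-sample t test with 95 % CI for difference was performed to evaluate differences between the two groups at baseline". This is the only confidence interval the plan names.
- For change, a two-way ANOVA "in EAT and other study variables between baseline, 3 and 6 months in both groups". No main effect, interaction or contrast is singled out as the primary test, and neither visit is named as primary.

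The Results paragraph of the Summary gives liraglutide EAT as 9.6 ± 2 mm at baseline, 6.8 ± 1.5 mm at 3 months and 6.2 ± 1.5 mm at 6 months, with p < 0.001 and reductions of 29% and 36%. For the other arm it says only "whereas there was no EAT reduction in the metformin group".

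The Conclusions then state that liraglutide added to metformin "caused an unprecedented, close to 40%, reduction of EAT" and describe the effect as rapid, "as the earliest reduction, of almost 30%, occurred within 3 months".

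**The concern.** The word caused makes this a claim about the difference between randomised arms. The number attached to it is the change within one arm. Under Study Criteria and Treatment Arms the plan records that "Both groups received lifestyle and diabetes education, as part of the standard care", so a before-after change in the liraglutide arm can include whatever happened under standard care. The effect of adding liraglutide is the liraglutide change minus the metformin change, and the second term is given only in words.

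A reader therefore cannot obtain the primary estimate or its precision from the report. Nor can the reader tell what p < 0.001 tests. If the ANOVA factors are group and visit, a visit main effect pools the arms, a group main effect averages in the baseline visit, and only the group-by-visit term addresses the stated primary outcome.

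Separately, the 6-month headline is higher than the within-arm figure printed in the Results paragraph just before it.

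**Working it through.** **1. The report's own percentages** (liraglutide means from the Summary, each rounded to 0.1 mm)

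- 3 months: (9.6 - 6.8)/9.6 = 29.2%. Rounding bounds: 1 - 6.85/9.55 = 28.3% and 1 - 6.75/9.65 = 30.1%. The printed 29% and the wording in the Conclusions both agree.
- 6 months: (9.6 - 6.2)/9.6 = 35.4%. Rounding bounds: 1 - 6.25/9.55 = 34.6% and 1 - 6.15/9.65 = 36.3%. The printed 36% lies inside.
- A within-arm 40% would need a 6-month mean of 0.60 × 9.6 = 5.76 mm, not 6.2 mm. Only the 6-month headline is out of line.

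**2. What the between-group result could be**

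It cannot be computed, because there are no metformin EAT values and no SD of change for either arm. The following is an illustration.

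From the Summary: n = 55 and 45; SDs 2 mm (baseline) and 1.5 mm (follow-up).

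Assumed, not in the documents: the same SDs in the metformin arm; baseline-to-visit correlation r = 0.5 (range 0.3 to 0.7); percentages taken of 9.6 mm as a fixed value.

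- SD of change = √(2² + 1.5² - 2·r·2·1.5) = 2.11, 1.80, 1.43 mm for r = 0.3, 0.5, 0.7.
- Half-width of the between-group 95% CI = 1.984 × SD × √(1/55 + 1/45) = 0.84, 0.72, 0.57 mm.
- Largest metformin change in either direction that a paired t test would call non-significant = 2.015 × SD/√45 = 0.63, 0.54, 0.43 mm.

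Net effect at 6 months:

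| Metformin change | r = 0.3 | r = 0.5 | r = 0.7 |
|---|---|---|---|
| Flat | 3.40 mm (CI 2.56 to 4.24), 35% | 3.40 mm (2.68 to 4.12), 35% | 3.40 mm (2.83 to 3.97), 35% |
| Non-significant fall | 2.77 mm (1.92 to 3.61), 29% | 2.86 mm (2.14 to 3.58), 30% | 2.97 mm (2.40 to 3.54), 31% |
| Non-significant rise | 3.40 + 0.63 = 4.03 mm, 42% | 3.40 + 0.54 = 3.94 mm, 41% | 3.40 + 0.43 = 3.83 mm, 40% |

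At 3 months a flat metformin arm gives 2.8 mm (CI 2.08 to 3.52 at r = 0.5). A non-significant fall gives 2.17 to 2.37 mm, with lower limits of 1.32 to 1.80 mm.

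**3. Against the plan's own yardstick**

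The sample-size sentence takes 1 "mm in EAT to be clinically significant". Every lower limit above exceeds 1 mm. If the metformin SD of change is 25% larger and metformin fell by the largest non-significant amount, the smallest lower limits are 1.64 mm at 6 months and 1.04 mm at 3 months.

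**4. What a net 40% would need**

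0.40 × 9.6 = 3.84 mm, so metformin EAT would have to rise by 3.84 - 3.40 = 0.44 mm (0.36 to 0.52 mm with rounding). That is about the size of the drift considered in step 2. The text neither reports nor excludes it.

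**The case against.** The strongest reply is that this is one abstract-style paragraph, that the analysis section does name an ANOVA covering both arms, and that missing detail in a summary does not show the comparison was not made. On the plain reading of the control-arm wording, metformin EAT did not fall, so subtracting it would not shrink the effect. The exact 36% is printed immediately before the looser headline.

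Much of this stands, and it rules out three stronger readings that a reader might infer:

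- **That p < 0.001 is a within-arm p-value, or that no between-group test was run.** It appears in the liraglutide clause, but its test is not identified. It may be the group-by-time term. All that can be said is that no p-value is identified as between-group.
- **That the true net effect is below the headline.** This would follow only if metformin EAT fell. The wording also permits a rise, which would put the net effect at about 40 to 42%. The drift limits themselves assume an unadjusted paired t test that the plan does not name; a multiplicity-adjusted comparison would widen them.
- **That the effect is in doubt, or that 36% is an error.** Neither is supported. The 36% reproduces within rounding, and the headline is loose upward rounding rather than a miscalculation.

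What the reply does not answer is that the Conclusions draw a causal, quantified inference from the within-arm change. The estimate that would support that inference, and its interval, are nowhere in the report. The Aim in the Summary could be read as a within-arm question, but the primary outcome in the Statistical Analysis section is explicitly between arms.

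**Conclusion.** The point holds as a gap in reporting and specification, and it should be fixed. The primary between-group estimate and its interval are absent, the primary ANOVA term is unnamed, and the Conclusions present a within-arm change of 35.4% (34.6 to 36.3%) as a treatment effect near 40%.

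An effect larger than 1 mm is not in doubt under the stated assumptions on metformin SDs, correlation and control-arm drift. The control-subtracted size at 6 months is about 35% if metformin was flat (95% CI about 28 to 43% at r = 0.5). It could be somewhat lower or higher otherwise, with point estimates of 29 to 42% across the cases shown. The text therefore does not settle the direction of any correction to the net effect. The mismatch between the headline and the report's own within-arm figure needs none of these assumptions.

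**What to change.** From the existing data:

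- Report the group-by-visit contrast for EAT at 3 and 6 months, in mm, with 95% CI and p-value. Use the two-way ANOVA with patient as a random factor, since the three visits are repeated measures on the same people, or an ANCOVA adjusted for baseline EAT.
- State that this contrast tests the primary outcome, and say which term gave p < 0.001. No primary visit was named, so label any choice of one as post hoc.
- Print metformin EAT mean and SD at baseline, 3 and 6 months.
- Replace the headline percentage with the between-group estimate and its CI. Give the within-arm change as about 35 to 36%, for description only.

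The cost is low: one contrast at two visits, one row of control values, one sentence on the ANOVA term and a reworded conclusion, provided the dataset is still available. The downside is a little extra analysis and possibly a less favourable headline. Trial conduct is unaffected.

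### The blinding statement for the primary EAT reading does not say that arm and visit were concealed from whoever took it, so detection bias in the size of the between-arm difference cannot be excluded

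*Combined protocol and SAP*

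**What the plan says.** All references are to the combined protocol and SAP.

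- **Study design:** "This was a randomized, open-label controlled 6-month study in 100 overweight/obese" subjects. Under Study Criteria and Treatment Arms, the add-on is a once-daily injection with nurse training, so patients know their arm.
- **Study Criteria and Treatment Arms:** the echocardiogram is a visit procedure, done alongside the examination and blood draw ("Each patient underwent a transthoracic echocardiographic study, full physical examination and a fasting blood drawn for measurement of blood glucose"). It recurs at "follow-up visits at 3 and 6 months and the same visit procedures were repeated at each follow-up visit".
- **Study procedures, Echocardiographic Epicardial Fat Thickness:** thickness is taken perpendicular to the right ventricular free wall at end-systole, at its maximum, and "The average value of three cardiac cycles was calculated and used for analysis". On masking, the text offers one sentence: "Echocardiograms were done by an experienced operator who was blinded to the patients' data". On quality control, it offers one: "Intra-observer reproducibility of echocardiographic measurement of EAT was assessed by the intra-class correlation coefficient". No value is given for that coefficient.
- **Statistical Analysis:** "Primary outcome of the study was EAT changes on liraglutide combined to metformin vs metformin monotherapy". A difference of 1 mm is taken as clinically significant.

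The document does not define what the operator's blinding covers. It does not say whether the scanner was also the reader, whether readings were live or offline, whether visit order was concealed, or whether patients were asked not to mention treatment.

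**The concern.** With patients and treating staff unmasked, the credibility of the primary comparison rests on the person who places the measurement. That person must choose the tissue borders, the end-systolic frame and the point of maximum thickness, so an expectation about the result can move the value by a fraction of a millimetre. An operator kept away from the chart still shares a room with a patient who knows the arm, and nothing described prevents disclosure.

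If readings at follow-up moved in one arm only, the shift would pass undiluted into the between-arm change, and no analysis of the same readings could remove it. Intra-observer agreement does not help: a reader who systematically reads lower in one arm can still agree closely with their own repeat readings. At stake is the size of the effect, which the Summary presents as its headline.

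**Working it through.** **1. The document's own figures.** From the Summary, liraglutide EAT went from 9.6 mm (SD 2) to 6.8 mm (SD 1.5) at 3 months and 6.2 mm (SD 1.5) at 6 months.

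- 3 months: 9.6 − 6.8 = 2.8 mm, and 2.8/9.6 = 29%, as reported.
- 6 months: 9.6 − 6.2 = 3.4 mm, and 3.4/9.6 = 35.4%, against 36% reported. Rounding of the means accounts for the gap.

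No metformin means are given, only that EAT did not fall there.

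**2. SD of change (assumed).** It is not reported. With SDs of 2 and 1.5 and within-patient correlation r, SD of change = √(2² + 1.5² − 2·2·1.5·r) = √(6.25 − 6r).

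- SD 2.0 mm corresponds to r = (6.25 − 4)/6 = 0.375.
- SD 1.5 mm corresponds to r = (6.25 − 2.25)/6 = 0.67.
- SD 1.0 mm corresponds to r = (6.25 − 1)/6 = 0.875.

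The ± 0.5 mm in the sample-size sentence, if it is meant as an SD, would need r = 1, so it is not used. The document describes its means and SDs as adjusted for age and sex, so these values are approximate.

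**3. Standard error.** For 55 and 45 patients, SE = SD × √(1/55 + 1/45) = SD × 0.201.

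**4. False-positive rate with no true effect and a differential reading shift b (assumed).** Rate = P(|Z + b/SE| > 1.96). This is a simple comparison of mean changes, not the two-way ANOVA that the document names.

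| SD of change (mm) | SE (mm) | b = 0.25 mm | b = 0.5 mm |
|---|---|---|---|
| 1.0 | 0.20 | 24% | 70% |
| 1.5 | 0.30 | 13% | 38% |
| 2.0 | 0.40 | 10% | 24% |

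The larger shift is half of the 1 mm that the document calls clinically significant.

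**5. Could such a shift account for the reported result?** Taking change on metformin as about zero, the smallest significant difference is 1.96 × SE = 0.59 mm at SD 1.5 and 0.79 mm at SD 2.0. The shift needed to remove significance runs from 2.8 − 0.79 = 2.0 mm to 3.4 − 0.59 = 2.8 mm, which is four to more than five times the 0.5 mm considered above.

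**6. Effect on the size.** If a 0.5 mm shift fell wholly in the liraglutide arm, it would make up 0.5/3.4 = 15% to 0.5/2.8 = 18% of the fall. It would be worth 0.5/9.6 = 5 percentage points of the relative reduction.

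**The case against.** The strongest reply is that assessor blinding is stated. In a report of an open-label trial, allocation is naturally among the patient data withheld from an operator, and no text shows that the mask failed. That stands: the defect is an undefined and unsecured mask, not an absent one. It does not close the point, because even on the generous reading nothing described keeps the patient from revealing the arm.

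A reader might go further in three directions that the document does not support.

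- **That the operator knew the visit and took the reading live.** The text says who did the echocardiograms but puts the measurement in the passive. Both steps are inference. In addition, knowing the visit without the arm would affect both groups alike and would not bias the between-arm contrast.
- **That drift in reading over the study distorts the result.** Drift common to both arms cancels in the primary comparison. The Summary reports no EAT reduction on metformin, which gives no sign of downward drift.
- **That visible weight loss revealed the arm.** The Summary gives no size for the BMI change and places it after 6 months, while 2.8 of the 3.4 mm fall was present at 3 months. The study nurse, not the operator, took the anthropometric measures.

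It is also fair to object that the shift sizes have no source in the document and that error rates under no true effect say little about a fall this large. That stands too. They show how sensitive a 1 mm threshold is, not what happened.

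**Conclusion.** The point holds as a gap in the description and protection of the primary measurement. The document does not establish that arm and visit were concealed from whoever took the reading, and its one reliability check cannot reveal a shift that differs by arm. Detection bias in the size of the between-arm difference therefore cannot be excluded.

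For a design aimed at 1 mm the sensitivity is material: 10% to 13% error for a 0.25 mm shift and 24% to 38% for 0.5 mm, if the SD of change lies between 1.5 and 2.0 mm. Both the shifts and the SD are assumptions.

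It would be wrong to conclude that the reported effect is a reading artefact. A plausible shift would not by itself produce a 2.8 to 3.4 mm fall. What remains open is how much of the stated size is real. This is an inexpensive improvement worth making, with medium confidence.

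**What to change.** **For a protocol of this design**, add text such as:

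> Right ventricular free-wall loops are stored at every visit. After follow-up is complete, or in batches of patients who have completed it, the same operator measures the loops offline with identifiers, dates, visit and treatment arm removed and the order shuffled. This value is the primary EAT measurement.

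**For the completed study**, leave the sentence on conduct as it is, since rewriting it would describe a procedure not known to have been done.

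- If the loops were archived, re-measure them as above and report the between-arm difference from both sets of readings.
- If they were not, report who took the readings and what was concealed from them, and state that masking to arm and visit cannot be assured.

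**Cost.** Storage, coding and offline reading of about 300 studies (100 patients × 3 visits) by the same operator, with no extra reader, visit or procedure. EAT values arrive later, but no rule in the document uses them during the study. For the completed study, feasibility depends on whether loops exist, which the document does not say. Offline reading removes bias in the reading, not bias in how the images were acquired.

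### One-predictor regression for determinants of HbA1c change leaves out baseline HbA1c and arm, so regression to the mean could pass for a determinant if baseline HbA1c or a close correlate is tested

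*Combined protocol and SAP*

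**What the plan says.** All of the analysis text is in one paragraph under STATISTICAL ANALYSIS. After naming change in epicardial fat (EAT) as the primary outcome, it says that "secondary outcomes were determinants of HbA1c changes during treatment". It does not list the candidate variables.

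The paragraph gives two methods that could bear on this outcome:

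- "Two-way ANOVA was used to calculate changes (Δ) in EAT and other study variables between baseline, 3 and 6 months in both groups". This compares visits and groups; it does not relate HbA1c change to a patient characteristic.
- "Relations between study variables were calculated using simple linear regression analysis". This is the only method for associations. It is not tied by name to the secondary outcome, but no other method is offered. The text does not say whether the regressions are run per arm or pooled.

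Age and sex adjustment is described for means only. No baseline HbA1c term, arm term or interaction is stated. Under Study Criteria and Treatment Arms, the baseline visit includes a "fasting blood drawn for measurement of blood glucose and haemoglobinA1c (HbA1c) and other parameters", and the same procedures are repeated at 3 and 6 months. The HbA1c used for eligibility (at most 8%) is a separate value, taken at least one month earlier.

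**The concern.** HbA1c change is follow-up minus baseline, so visit-to-visit noise in the baseline value enters the change with a minus sign. A patient whose baseline reading was high by chance will tend to show a fall, and one whose reading was low by chance will tend to show a rise. A one-predictor regression of change on baseline HbA1c reads this as a relation. A candidate that follows the measured baseline value inherits part of it.

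This is not confounding by arm. It arises inside the liraglutide arm alone, and adding an arm term leaves the slope where it was. It is a bias and not a chance finding, so a multiplicity correction would not remove it. The risk is that a reader takes such a slope as showing which patients gain most from liraglutide, when the same slope would be expected on metformin.

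**Working it through.** **The plan's own figure.** There is none for this outcome. The stated 90% power concerns EAT only and does not bear on this point.

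**Inputs.** From the documents: 55 liraglutide and 45 metformin patients (SUMMARY), two-sided 5% level, entry HbA1c at most 8% on an earlier sample. Assumed: r, the correlation of baseline and follow-up HbA1c, from 0.6 to 0.9; and k, follow-up SD divided by baseline SD, equal to 1 unless stated. In every scenario change has no true link to underlying HbA1c.

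**Formulas.** For change = follow-up − baseline, regressed on baseline:

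- slope = r·k − 1
- correlation = (r·k − 1) / √(k² + 1 − 2·r·k), which is −√((1 − r)/2) when k = 1
- chance of p<0.05 by Fisher's z: Φ(z − 1.96) + Φ(−z − 1.96), where z = atanh(|correlation|)·√(n − 3)

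Example for r = 0.8, n = 55: correlation = −√(0.2/2) = −0.316; atanh(0.316) = 0.327; z = 0.327 × √52 = 2.36; Φ(2.36 − 1.96) = 66%.

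For a candidate linked to change only through the measured baseline value, and correlated 0.6 with it, the correlation with change is 0.6 times the one above. For r = 0.8 that is 0.6 × −0.316 = −0.190.

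| r | Slope | Correlation | Baseline HbA1c, n=55 | Baseline HbA1c, n=45 | Candidate correlated 0.6, n=55 |
|---|---|---|---|---|---|
| 0.6 | −0.40 | −0.447 | 93% | 88% | 51% |
| 0.7 | −0.30 | −0.387 | 84% | 75% | 40% |
| 0.8 | −0.20 | −0.316 | 66% | 56% | 28% |
| 0.9 | −0.10 | −0.224 | 37% | 31% | 16% |

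Simulations agree within a few points: about 94% down to 36–38% for baseline HbA1c, and about 50% down to 15–16% for the correlated candidate.

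**Entry cut-off.** The table ignores selection. Simulating entry at 8% on a separate earlier value (assumed mean 7.1%, SD 0.7% before selection) gives about 96% at r = 0.6, falling to 44–50% at r = 0.9 (the range over repeated simulations), in the 55-patient arm. Here r is the value before selection; 0.6, 0.7, 0.8 and 0.9 become about 0.55, 0.65, 0.76 and 0.87 among those enrolled. The correlations in the table should therefore not be paired with these higher rates.

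**Arm term.** With all 100 patients, no cut-off and an arm term, simulated rejection rates for baseline HbA1c are 98%, 91% and 60% at r = 0.7, 0.8 and 0.9. The mean slopes are −0.30, −0.20 and −0.10, the same as without the arm term.

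**Unequal SDs.** At r = 0.8 and k = 1.25, slope = 0.8 × 1.25 − 1 = 0 and the artefact is gone. At r = 0.9 and k = 1.25, slope = 1.125 − 1 = +0.125, so the sign reverses. At k = 0.75 the artefact is stronger than in the table.

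**Other candidates and the remedy.** In simulation at r = 0.7, n = 55, a candidate correlated 0, 0.3 or 0.6 with measured baseline HbA1c is significant in 5%, 13% or 42% of runs under simple regression. With baseline HbA1c added, the rates are 5%, 6% and 4%. The arm-by-baseline interaction test for 6-month HbA1c rejects in 4.6 to 5.7% of runs.

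**The case against.** The strongest objection is that the plan never calls for the analysis at fault. Baseline HbA1c is not named as a candidate, the regression sentence is not attached to the secondary outcome, and measuring HbA1c at baseline is not the same as using it as a predictor. This stands, and it makes the point conditional. It does not remove it: no candidate is excluded, and no other association method is given.

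A second objection is that a negative slope is not inevitable. This also stands. The slope is r·k − 1, neither r nor k is in the documents, and a response that varies between patients could widen the follow-up SD in the liraglutide arm.

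Third, the figures for a correlated candidate assume that it tracks the measured baseline value, visit noise included. A candidate tied only to the stable HbA1c level would not show this artefact in a simple regression. That is a fair limit on those figures.

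Fourth, determinants can mean prognostic correlates. Requiring an arm-by-variable interaction for each of them would turn the question into effect modification, which the plan does not claim to study. This stands and shapes the fix.

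Last, the SUMMARY reports no determinant of HbA1c change and no regression result, so no conclusion visible in the document rests on such a slope.

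**Conclusion.** The concern holds in conditional form. For its secondary outcome the plan offers only one-predictor regression, without baseline HbA1c or arm. If baseline HbA1c or a variable tracking its measured value is tested that way, an association is expected with no true link. With equal SDs and r from 0.6 to 0.9, the chance of p<0.05 in the 55-patient arm is about 94% down to 36% for baseline HbA1c without the entry cut-off, 96% down to 44% with it, and about 50% down to 15% for a candidate correlated 0.6 with baseline.

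A reader might infer that baseline HbA1c is bound to emerge as a determinant, or that the plan followed as written would very probably report it. The documents do not support either: they list no candidates, the slope can be zero or positive if the follow-up SD is larger, and at r = 0.9 significance within the arm is at best about even. Nor do they support an inference that the primary EAT comparison is affected. The matter is worth correcting, but it is confined to a loosely described secondary outcome.

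**What to change.** Replace the simple regression for the secondary outcome with a model of 6-month HbA1c on arm, baseline HbA1c and the candidate, and list the candidates. Read the candidate's coefficient as an association with 6-month HbA1c among patients with the same arm and measured baseline. Do not report the slope of HbA1c change on baseline HbA1c as a determinant.

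Only if the trial wishes to claim that baseline HbA1c or another variable determines response to liraglutide specifically should that claim rest on the arm-by-variable term. Its low precision at 55 versus 45 should then be stated.

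The document is written as a final report, so in practice this means a sentence of text and a re-run on data already collected, or a caveat if no re-run is done. No new patients or visits are needed. The downside is that fewer determinants will be declared.
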